## 5. RANDOMISATION AND ENROLMENT PROCEDURE

### 5.1 Randomisation practicalities

All randomisation and enrolment will occur during routine working hours – as all research visits will take place in the Biomedical Research Unit during the week between 9am and 5pm. Children will be recruited when they are clinically well, not during an acute attack.

We will use the Imperial INFORM database Unit to undertake randomisation

We wish to stratify randomisation according to sex and age, to achieve similar numbers of boys and girls in each group, and to have a similar average age for each group.

The age stratification will be as follows: >1-  $\leq$ 3 years and >3 -  $\leq$ 5 years

As wheezing in preschool children is a seasonal disorder (majority of symptoms and exacerbations occur between September – April each year), the baseline assessments and pre-randomisation visits will be arranged between late August – December each year, so that randomisation and intervention take place between September – January each year, to allow the 4 month intervention period to fall within the main season.

All patients will be given a study specific 24hrs emergency contact card immediately after being randomised. The card includes details of the study: Study title, patient trial number, CI/PI's contact details along with out of hours contact details in case of emergency.

### 5.2 Unblinding

The trial is a single blind trial. The parents of the children taking part and the physicians that decide the clinical management will be unaware of the arm the child has been randomised to, but the researcher will know – since the researcher will have to instruct the family on which treatment should be initiated once randomisation has occurred.

We do not foresee a need to unblind as there are no new treatments being trialled, we are using licenced treatments but with a novel indication. All doses to be used are also within licenced indications.

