## REFERENCE DIAGRAM OF TRIAL DESIGN:

## 1. INTRODUCTION

### 1.1 BACKGROUND

At least one-third of all children under 5 years suffer from wheezing and breathlessness, but despite the high incidence, there are few effective therapies. Current guidelines recommend the management of preschool wheezing should be determined by clinical phenotype. However, this is based predominantly on expert consensus with little evidence. The two clinical phenotypes are episodic wheeze, in which wheeze occurs during discrete episodes, usually in association with an upper respiratory tract infection, with no symptoms in between, and multiple trigger wheezing, with discrete episodes and symptoms in between. The current approach has several limitations: i) It relies on accurate parental reporting of symptom pattern, which may not always be clearly distinguishable as episodic or multiple trigger. ii) Clinical phenotypes may switch within patients in a short period, such as only 3 months. iii) The underlying infectious cause of acute episodes is not considered. Although it was previously thought that most episodes are precipitated by viral infections, it is now recognised that an equal number are also caused by bacterial infection. The current guidelines have not been compared to other strategies. It is essential that the correct approach is adopted since therapeutic options include steroids, which if administered incorrectly result in adverse effects, the most worrying in the preschool age-group being reduced growth.

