#### **Management in the pathological phenotype arm:**

##### **1. Eosinophilic inflammation, no bacterial infection:**

Children with sputum eosinophils  $>2.4\%$  or blood eosinophils  $\geq 3\%$  will be defined as eosinophilic and management will be as follows:

- i) Regular inhaled steroids (beclometasone 200 mcg bd) for 4 months in those previously not on any regular therapy.
- ii) Of children who have already been prescribed inhaled steroid therapy, those with an eosinophilic phenotype will continue for a further 4 months.
- iii) Children who have already been prescribed a regular leukotriene receptor antagonist will continue this and regular inhaled steroids (beclometasone 200mcg bd) will be added to their maintenance therapy for 4 months.
- iv) Use of as required bronchodilator therapy will continue

**2. Non-eosinophilic, no inflammation, no infection:** Children with either sputum eosinophils  $\leq 2.4\%$  or blood eosinophils  $< 3\%$  will be defined as non-eosinophilic and management will be as follows:

- i) Use of as required bronchodilators for acute symptoms
- ii) Non-eosinophilic children that have already been prescribed regular inhaled steroids will be asked to stop them for 4 months

Children with no bacterial growth from oropharyngeal swab or induced sputum, and without eosinophilic inflammation will continue management according to the non-eosinophilic, no inflammation, no infection profile.

3. **Bacterial infection, no eosinophilic inflammation:** Children with a positive bacterial culture result from oropharyngeal swab or induced sputum will be treated with a 4 week course of antibiotics. Four weeks of antibiotic therapy will be used as this has been shown to be beneficial in a previous study of severe preschool wheeze. If these children have already been prescribed regular inhaled steroids, they will be stopped for 4 months.
4. **Eosinophilic inflammation AND bacterial infection:** Children with raised eosinophils in induced sputum or blood AND positive bacterial culture will be managed according to the eosinophilic inflammation alone guideline. They will only be given inhaled steroids for 4 months, and no antibiotics. This is to assess only one intervention at a time. However, we do not anticipate many children will be in this group as our previous data shows those with positive bacterial cultures are very unlikely to have eosinophilia.

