#### **Management in the clinical guidelines arm:**

The children will be treated as directed by their Consultant Paediatrician. The prescription for the drugs to be used will be dispensed from the pharmacy department at the Royal Brompton Hospital – as directed by the clinician. Usually only 2 weeks of medication is prescribed by the pharmacy, but for this trial 4 months' supply will be given.

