### **8.4 SUBSEQUENT ASSESSMENTS**

Children will not routinely be brought back for follow-up during the 4 month intervention period.

Their compliance with the treatment prescribed will be monitored using electronic monitoring devices for the inhaled treatment, and by weekly telephone calls by the research nurse to remind the family of the importance of making sure the treatment is given daily for the period prescribed.

A symptoms diary will not be kept by the parents during the intervention period, but an automated text will be sent to the parents daily asking whether or not their child had any

symptoms of wheeze in the last 24 hours – the answer to the text will be a simple “yes” or “no” response.

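### The blinding of parents claimed in section 5.2 is not secured for some phenotype-arm families, and the parent-dependent primary count has no stated protection against knowledge of treatment

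*Combined protocol and SAP*

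**What the plan says.** The Study Summary and section 3 label the trial single blind. Section 5.2 repeats it ("The trial is a single blind trial") and explains that parents and the physicians who decide management "will be unaware of the arm the child has been randomised to, but the researcher will know". The reason given for the researcher's knowledge is "since the researcher will have to instruct the family on which treatment should be initiated once randomisation has occurred".

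Section 6.1 sets out what phenotype-arm families are told:

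- Item 2: "Non-eosinophilic children that have already been prescribed regular inhaled steroids will be asked to stop them for 4 months".
- Item 3: children with a positive culture and no eosinophilia "will be treated with a 4 week course of antibiotics", and any regular inhaled steroid is stopped for 4 months.

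In the clinical guidelines arm, "The children will be treated as directed by their Consultant Paediatrician". Section 1.1 lists as a limitation of the current approach that "The underlying infectious cause of acute episodes is not considered".

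The primary outcome is the number of unscheduled healthcare visits in 4 months (section 3.1). Section 4.4 leaves families to take an ill child to be seen as they usually would. Section 3 has families telephoned weekly about these visits, and section 8.4 says that the visits are recorded in the weekly calls and asked about again at the 4-month visit. Section 8.4 also describes "weekly telephone calls by the research nurse to remind the family of the importance of making sure the treatment is given" daily. Under Assessment of compliance, the reminder refers to whichever treatment the child has, inhaler or antibiotic.

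**The concern.** Section 5.2 states a protection that other sections do not deliver for every family. A parent whose child is kept off a previously prescribed inhaled steroid may seek care more readily. A parent given a targeted antibiotic may seek care less readily. A caller who knows the treatment may probe or record differently. Any of these would move the primary count without a change in disease.

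Two things are at stake. A report calling the trial single blind would overstate how well the comparison was protected. And because the study is meant to inform the size of a larger trial (Study Summary, section 8.6), a distorted visit rate or difference would carry forward into that calculation.

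**Working it through.** **Passages side by side**

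1. *Can the family infer the arm?* All drugs are open and no sham is described. The two instructions in section 6.1, items 2 and 3, are visible to parents and follow from the phenotype rules. They are strong cues for those families only.
2. *Does the outcome depend on the family?* Partly: an unscheduled visit starts with a decision to seek care (section 4.4).
3. *Is the collector separated from treatment knowledge?* No. The weekly caller discusses the child's treatment (Assessment of compliance, section 8.4). Section 5.2 speaks of the researcher and section 8.4 of the research nurse. The documents neither equate nor separate the two.
4. *Is there another safeguard?* No outcome assessor without the allocation and no check of visit counts against records is described. Section 8.5 uses the GP and local hospital only to trace a change of address. Section 9.0 does not address the matter.

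**The plan's own figure.** The plan gives no figure for blinding. Its only design figure is 36 per group (section 3, Number of subjects), and no standard deviation, dispersion or sidedness is stated. With Poisson counts, a one-third reduction, two-sided 5% and 80% power:

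n = (1.96 + 0.84)² × (1/λ0 + 1/λ1) / (ln 2/3)²

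- Annual rates 5 and 3.33: 24 per group.
- 4-month rates 1.67 and 1.11: 72 per group.

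Neither is 36, so an input is missing. The plan itself says that the number is not a precise power calculation. I therefore take 36 and 50 per group as given; the point does not depend on how they were derived.

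**Illustration of size**

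Inputs: 5 attendances per child per year, spread evenly, gives λ0 = 5/3 = 1.67 per 4 months. The target of one-third is 1.67/3 = 0.56 visits. A 10% shift is 0.17 visits, and 0.167/0.556 = 30% of that target.

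Assumptions not in the documents: Poisson counts, no true treatment effect, and a net ratio b between arms caused only by attendance or recording.

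- SE = √[(1/λ0 + 1/(bλ0))/n]
- θ = |ln b|/SE
- Rejection rate = Φ(θ − 1.96) + Φ(−θ − 1.96)

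Worked case, b = 0.90 and n = 36: SE = √[(0.600 + 0.667)/36] = 0.188; θ = 0.105/0.188 = 0.56; rate = Φ(−1.40) + Φ(−2.52) = 8.7%.

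| Net difference | 36 per group | 50 per group |
|---|---|---|
| 5% | 5.9% | 6.2% |
| 10% | 8.7% | 10.2% |
| 20% | 21.1% | 27.4% |

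If the variance is 1.5 times the mean and the standard error allows for it, the 10% row becomes 7.4% and 8.4%, and the 20% row 15.6% and 19.8%.

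The net difference is a whole-arm average. If half the arm shifted by 10%, the net would be 0.5 × 10% = 5%. If equal parts shifted up and down by the same amount, the net would be zero.

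**The case against.** Several stronger readings are tempting, and the documents do not support them.

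- *A reader might infer that long antibiotics or stopping steroids can occur only in the phenotype arm.* The control arm is whatever the Consultant directs, with no bar on either, and sections 4.4 and 11.3 let clinicians change treatment in both arms. Section 1.1 describes a weakness of the guideline approach, not what these Consultants prescribe. Children in both arms who take inhaled steroids are asked to stop for 2 weeks before the research visit (section 8.2), so the cue is being told to stay off them.
- *A reader might infer that the whole trial is unblinded.* Eosinophilic children start or continue an ordinary inhaler. Uninfected, non-eosinophilic children not already on inhaled steroids use bronchodilators as required. Either can look like usual care.
- *A reader might infer that the Consultant can tell the arm.* The Consultant determines the clinical phenotype before randomisation, the researcher passes on the instruction, and drugs for both arms come from the same pharmacy. Whether the Consultant could work it out is unclear.
- *A reader might take the rejection rates as the trial's actual error rate.* The shifts are assumed, they apply to the whole arm in one direction, and section 9.0 does not clearly make a Poisson test the planned group comparison.

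It is also fair to say that blinded outcome assessment is never claimed, that this is a proof-of-concept study, and that some behaviour follows from knowing the treatment, which masking the arm alone would not remove.

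These points limit the reach of the concern. They do not restore the assurance in section 5.2, and the study still states an efficacy hypothesis on this outcome (section 1.2, Hypothesis).

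**Conclusion.** The point holds in a limited form. The stated blinding of parents is not secured for phenotype-arm families who receive either of the two visible instructions, and the primary count, partly driven by parents and collected by staff who know the treatment, has no described safeguard. For treating physicians, the documents do not settle the question.

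Neither the size nor the direction of bias can be known from the documents. Under the stated assumptions, a net 5% difference would barely matter (about 6% rejection at either sample size). A net 20% difference would matter a great deal (about 21% with 36 per group, 27% with 50). Recruiting more children makes a fixed bias easier to mistake for an effect. This should be corrected in wording and outcome collection; it is not a reason to abandon open treatment.

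**What to change.** 1. In the Study Summary and section 3, replace the single blind label, and in section 5.2 replace the claim that parents and physicians will be unaware. Suggested wording: *partially blinded: allocation not disclosed to families but inferable from treatment*. Limit the conclusions accordingly.
2. In sections 3 and 8.4, specify one scripted weekly call for every child in both arms, including children given no study drug. Ask the date, place and reason of each healthcare contact before any treatment reminder. Make that record the source of the primary count.
3. Have an existing team member, confirmed not to hold the allocation, classify each contact as unscheduled or not from a listing with arm and treatment removed, before the arms are compared. Section 12.0 does not say whether the trial statistician holds the allocation, so this must be checked and not presumed. The step protects classification only; it cannot correct attendance behaviour.
4. State that the primary result will be interpreted alongside hospital admissions and oral-steroid days. Both are already secondary outcomes, so this adds no data collection. They are less parent-driven, though not immune.

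The cost is protocol wording, a call script and a little extra data handling, with no new staff and no change to any treatment. The trial gives up the plain single blind label.

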## 6. TREATMENTS

### 6.1 Treatment arms

The drugs to be used in the pathological phenotype arm include:

Beclometasone dipropionate metred dose inhaler with spacer – 100mcg per dose – 2 puffs twice a day

or

Antibiotics – augmentin duo (0.3ml/kg bd) or azithromycin (10mg/kg od) – therapeutic dose calculated according to the child's weight – for 4 weeks. The actual antibiotic used will be determined by the sensitivities of the organisms identified on bacterial culture. For children that are allergic to penicillin, azithromycin will be used instead of augmentin duo.

The drugs will be dispensed from the pharmacy at The Royal Brompton Hospital. If antibiotics are needed, a 4 week supply will be dispensed, and all children will be prescribed 4 weeks of therapy.

If the beclometasone inhaler is needed, sufficient doses for 4 months will be dispensed.

#### **Management in the pathological phenotype arm:**

##### **1. Eosinophilic inflammation, no bacterial infection:**

Children with sputum eosinophils  $>2.4\%$  or blood eosinophils  $\geq 3\%$  will be defined as eosinophilic and management will be as follows:

- i) Regular inhaled steroids (beclometasone 200 mcg bd) for 4 months in those previously not on any regular therapy.
- ii) Of children who have already been prescribed inhaled steroid therapy, those with an eosinophilic phenotype will continue for a further 4 months.
- iii) Children who have already been prescribed a regular leukotriene receptor antagonist will continue this and regular inhaled steroids (beclometasone 200mcg bd) will be added to their maintenance therapy for 4 months.
- iv) Use of as required bronchodilator therapy will continue

**2. Non-eosinophilic, no inflammation, no infection:** Children with either sputum eosinophils  $\leq 2.4\%$  or blood eosinophils  $< 3\%$  will be defined as non-eosinophilic and management will be as follows:

- i) Use of as required bronchodilators for acute symptoms
- ii) Non-eosinophilic children that have already been prescribed regular inhaled steroids will be asked to stop them for 4 months

Children with no bacterial growth from oropharyngeal swab or induced sputum, and without eosinophilic inflammation will continue management according to the non-eosinophilic, no inflammation, no infection profile.

3. **Bacterial infection, no eosinophilic inflammation:** Children with a positive bacterial culture result from oropharyngeal swab or induced sputum will be treated with a 4 week course of antibiotics. Four weeks of antibiotic therapy will be used as this has been shown to be beneficial in a previous study of severe preschool wheeze. If these children have already been prescribed regular inhaled steroids, they will be stopped for 4 months.
4. **Eosinophilic inflammation AND bacterial infection:** Children with raised eosinophils in induced sputum or blood AND positive bacterial culture will be managed according to the eosinophilic inflammation alone guideline. They will only be given inhaled steroids for 4 months, and no antibiotics. This is to assess only one intervention at a time. However, we do not anticipate many children will be in this group as our previous data shows those with positive bacterial cultures are very unlikely to have eosinophilia.

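### Section 6.1 defines non-eosinophilic in a way that overlaps with eosinophilic, so a culture-negative child with one raised and one unraised marker gets opposite inhaled-steroid instructions

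*Combined protocol and SAP*

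**What the plan says.** All of the following is in section 6.1, under management in the pathological phenotype arm.

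- Item 1 gives the positive class: "Children with sputum eosinophils $>2.4\%$ or blood eosinophils $\geq 3\%$ will be defined as eosinophilic". These children start beclometasone for 4 months, or have it added to a regular leukotriene receptor antagonist. For those already on inhaled steroid: "Of children who have already been prescribed inhaled steroid therapy, those with an eosinophilic phenotype will continue for a further 4 months".
- Item 2 gives the negative class: "Children with either sputum eosinophils $\leq 2.4\%$ or blood eosinophils $< 3\%$ will be defined as non-eosinophilic". These children use bronchodilators as required. For those already on inhaled steroid: "Non-eosinophilic children that have already been prescribed regular inhaled steroids will be asked to stop them for 4 months".
- Item 2 is headed "Non-eosinophilic, no inflammation, no infection". Its closing sentence sends to this management the following group: "Children with no bacterial growth from oropharyngeal swab or induced sputum, and without eosinophilic inflammation will continue management".
- Item 3 (antibiotics for 4 weeks, any inhaled steroid stopped) is headed "Bacterial infection, no eosinophilic inflammation".
- Item 4 reads: "Children with raised eosinophils in induced sputum or blood AND positive bacterial culture will be managed according to the eosinophilic inflammation alone guideline".

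Section 4.1 plans a full blood count and sputum induction for every participant. Section 8.2 reports sputum induction success of up to 95%. Under Number of subjects in section 3, an evaluable child needs at least a blood sample and an oropharyngeal swab; sputum is not required.

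**The concern.** Items 1 and 2 should divide the children into two separate classes. Item 1 joins its two conditions with *or*. Its complement must therefore join the reversed conditions with *and*, but item 2 uses *either … or*. A child with one marker above its cut-off and the other below satisfies both sentences. The two sentences are equally operative, since each is worded as a definition, and nothing says which prevails.

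This rule decides who receives inhaled steroid, so it is part of the experimental intervention itself. Under section 5.2 the researcher tells the family which treatment to start. Under section 8.4 children are not routinely seen again during the 4 months, although weekly calls continue. If item 2's sentence were applied to a discordant child, steroid would be withheld or stopped in a child whom item 1 says should have it. Inconsistent handling would also blur which strategy was tested, and so what the larger trial would take forward.

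**Working it through.** The plan gives no figure to reproduce here. The check is one of logic.

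**Inputs (section 6.1).** Let S be sputum eosinophils (%) and B blood eosinophils (%).

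- Item 1, eosinophilic: E = (S > 2.4 or B ≥ 3).
- Item 2, non-eosinophilic as printed: N = (S ≤ 2.4 or B < 3).
- True complement of item 1: not E = (S ≤ 2.4 and B < 3).

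**Step 1. Values on each side of the cut-offs, both markers measured.**

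| S | B | Item 1 (E) | Item 2 as printed (N) | Item 2 with *and* |
|---|---|---|---|---|
| 2.4 | 2.9 | no | yes | yes |
| 2.4 | 3.0 | yes | yes | no |
| 2.5 | 2.9 | yes | yes | no |
| 2.5 | 3.0 | yes | no | no |

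As printed, 2 of the 4 patterns fall in both classes, and these are the two discordant ones. With *and*, each pattern falls in exactly one class, with no overlap and no gap.

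**Step 2. Blood result only.** B = 2.9 gives N alone and B = 3.0 gives E alone. There is no conflict, so the problem needs both markers to be available. Sections 4.1 and 8.2 make that the expected situation for many children.

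**Step 3. Instructions for a discordant, culture-negative child.**

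| Existing treatment | Item 1 | Item 2 |
|---|---|---|
| No regular therapy | start inhaled steroid for 4 months | bronchodilator as required only |
| Inhaled steroid | continue for 4 months | stop for 4 months |
| Leukotriene receptor antagonist | add inhaled steroid for 4 months | no inhaled steroid added |

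The two columns disagree in every row.

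**Step 4. Discordant, culture-positive child.** Item 4 covers this child directly: raised eosinophils in sputum or blood with a positive culture means steroid alone. Item 3 is limited by its heading to children without eosinophilic inflammation. If item 2's definition supplied the meaning of that heading, the child would also fall under item 3 (antibiotics, steroid stopped) and would conflict with item 4. Whether there is a conflict here depends on how the headings are read.

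**The case against.** The strongest reply is that the intent is plain. Item 2's heading and closing sentence confine it to children without eosinophilic inflammation. Item 4 counts a raised result in either sample. Arm ii in the Study Summary and objective 1 in section 2 also treat blood or sputum as sufficient (I cite these for that logic only, not for cut-offs). All of this points to one rule: any raised marker is eosinophilic. That stands, and it limits the seriousness of the point. It does not remove a numerical definition that says otherwise.

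A second reply is that *either … or* means whichever sample is available, since sputum may be missing. For children with one result that reading works and gives exact complements. It does not settle the child with two conflicting results, to whom the printed sentence also applies.

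Third, exposure is limited. Section 23's equivalent in the plan, section 4, places research visits, randomisation and dispensing at one hospital, so there is little scope for sites to apply different rules, and the trial is a proof of concept. This also stands.

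A reader might go further and infer an exact share of treatment profiles in conflict, with culture-positive children wholly clear. The documents do not support that. If headings limit scope, item 2's heading removes the culture-negative conflict as well. If item 2's definition carries over into item 3, culture-positive children are drawn in. Any such count depends on the reading chosen.

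**Conclusion.** Item 2 is wrong as written. With both markers measured, 2 of the 4 patterns meet both definitions, and a culture-negative child with either of these patterns receives opposite inhaled-steroid instructions. This rests only on the printed wording of items 1 and 2 and on the absence of any precedence rule.

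Its practical size is unknown. The documents give no rate of discordance between blood and sputum, and a count of patterns is not a count of children, so I offer no estimate.

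A reader might infer that the trial's comparison is compromised or that the design intent is unclear. Neither follows. The randomised intention-to-treat comparison stands whichever rule is applied, and the intended rule can be inferred. This is an internal inconsistency in the treatment-assignment rule. It should be corrected, but it does not undermine the design.

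**What to change.** Replace item 2's definition in section 6.1 with wording such as:

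*A child is non-eosinophilic if sputum eosinophils are 2.4% or lower and blood eosinophils are below 3%; if no sputum was obtained, blood eosinophils below 3% suffice. A child with either marker raised is eosinophilic. These definitions also apply to items 3 and 4.*

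The last sentence closes the culture-positive question in step 4. The clause on missing sputum keeps the class that blood-only children already have. The cost is a short change to the protocol text, with no new sample, procedure or visit.
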